2 STUDY OBJECTIVES

2.1 OBJECTIVES

2.1.1 Primary Objective

This study aims to investigate the effect of early CTCA in patients with suspected or confirmed ACS presenting to the ED, MAU, or cardiology, upon interventions, event rates and health care costs in a pragmatic clinical trial and economic evaluation up to 1 year after the trial intervention. The primary objective will be to investigate the effect of the intervention by comparing all-cause death or subsequent non-fatal type 1 or type 4b MI at one year.

2.1.2 Secondary Objectives

1. The proportion of patients receiving coronary angiography and revascularisation at index hospitalisation and during 12-month follow up.
2. The proportion of patients representing or readmitted to hospital with suspected ACS/recurrent chest pain up to one year after index presentation.
3. The use of cardiovascular treatment during index hospitalisation and preventative therapies on discharge.
4. Length of stay at index hospitalisation.
5. The use of NHS resource including hospitalisation and other investigations and interventions.
6. The proportion of patients with symptoms, morbidity and mortality up to one year.
7. Quality of life.
8. The incremental cost per QALY gained by providing CTCA compared to current standard practice.

2.2 ENDPOINTS

2.2.1 Primary Endpoint

The **primary end-point** will be all-cause death or subsequent non-fatal type 1 or type 4b MI at one year, measured as time to first such event. MI will be defined according to the most recent Universal Definition [Thygesen K, 2012] and will be adjudicated by two independent cardiologists blinded to the intervention.

2.2.2 Secondary Endpoints

Key Secondary Endpoints

1. Coronary Heart Disease (CHD) death or subsequent non-fatal MI;
2. Cardiovascular Disease (CVD) death or subsequent non-fatal MI;
3. Subsequent Non-fatal MI;
4. Coronary Heart Disease death;
5. Cardiovascular death;
6. All-cause death.

Other Endpoints

- Coronary Heart Disease (CHD) death or subsequent non-fatal MI (type 1 or 4b);
- Subsequent Non-fatal MI (type 1 or 4b);
- Non-cardiovascular death;
- Invasive coronary angiography;
- Coronary revascularisation;
- Percutaneous coronary intervention;
- Coronary artery bypass graft;
- Proportion of patients prescribed ACS therapies during index hospitalisation;
- Proportion of patients discharged on preventative treatment or have alteration in dosage of preventative treatment during index hospitalisation;
- Length of stay for index hospitalisation;
- Representation or rehospitalisation with suspected ACS/recurrent chest pain within 12 months after index hospitalisation;

- Chest pain symptoms up to 12 months;
- Patient satisfaction at 1 month;
- Clinician certainty of presenting diagnosis after CTCA;
- Quality of Life (measured by EQ-5D-5L up to 12 months).

Adverse Events and Serious Adverse Events:

- Proportion of patients with alternative cardiovascular diagnoses identified on CTCA;
- Proportion of patients with non-cardiovascular diagnosis identified on CTCA ;
- Radiation exposure from CTCA as trial intervention.

Cost effectiveness:

- Estimated in terms of the lifetime incremental cost per quality-adjusted life year (QALY) gained.

3 STUDY DESIGN

RAPID-CTCA is an open prospective parallel group randomised controlled trial of CTCA and standard care or standard care only in patients presenting to the ED, MAU, or cardiology with suspected or confirmed ACS. Recruitment will take place in ~35 NHS tertiary and district hospitals (with and without on-site invasive coronary angiography facilities) with emergency departments, acute medical, radiology and cardiology services. Participants will be randomised to CTCA and standard care, or standard care only. Participants allocated CTCA will receive the scan during the initial admission or if discharged, as an ambulatory patient within 72 hours of randomisation (see section 5.4.2). All participants will be followed up for one year and be asked to complete questionnaires at baseline, 1, 6 and 12 months to assess quality of life, angina symptoms and NHS services usage.

4 STUDY POPULATION

4.1 NUMBER OF PARTICIPANTS

Our original sample size calculation was based on an estimated one-year death or subsequent MI rate for this patient group of ~20% [Mills N et al, 2011]. 2424 evaluable patients were, therefore, required (1212 per arm) to have 90% power to detect a 20% vs.15% difference in one-year death or subsequent MI rate, 2-sided $P<0.05$. With a 3% drop out rate, the sample size would have been 2,500 patients. However, on review, after recruiting and following up the first 716 participants the overall event rate was 6.8% (95% confidence interval 5.2% to 8.9%). In addition, we were recruiting at a significantly lower rate than originally predicted. As part of an extension application the above information was used to calculate a variety of sample sizes for a range of event rates (6%, 6.8% and 8%) and effect sizes (Relative Risk 0.5, 0.6, 0.75) with 80% and 90% power. The only plausible sample size option given recruitment rates with associated trial fatigue and potential for loss of clinical equipoise, event rates and funding was to deliver a trial of at least 1720 patients (not allowing for missing data), at least 1735 with expected loss to follow up rates, which would provide the trial the opportunity to detect a 3.4% ARR at the current primary event rate of 6.8% with 80% power, 2-sided $P<0.05$.

4.2 INCLUSION CRITERIA

Patient ≥ 18 years with symptoms mandating investigation for suspected or confirmed ACS with at least one of:

- ECG abnormalities e.g. ST segment depression >0.5 mm;
- History of ischaemic heart disease (where the clinician assessing patient confirms history based on patient history or available records);

- Troponin elevation above the 99th centile of the normal reference range or increase in high sensitivity troponin meeting European Society of Cardiology criteria for 'rule-in' of myocardial infarction (NB troponin assays will vary from site to site; local laboratory reference standards will be used).

4.3 EXCLUSION CRITERIA

1. Signs, symptoms, or investigations supporting high-risk ACS:
 - ST elevation MI;
 - ACS with signs or symptoms of acute heart failure or circulatory shock;
 - Crescendo episodes of typical anginal pain;
 - Marked or dynamic ECG changes e.g. ST depression of >3 mm
 - Clinical team have scheduled early invasive coronary angiography on day of trial eligibility assessment.
2. Patient inability to undergo CT:
 - Severe renal failure (serum creatinine >250 µmol/L or estimated glomerular filtration rate <30 mL/min);
 - Contrast allergy;
 - Beta blocker intolerance (if no alternative heart rate limiting agent available/suitable) or allergy;
 - Inability to breath hold;
 - Atrial fibrillation (where mean heart rate is anticipated to be greater than 75 beats per minute after beta blockade).
3. Patient has had invasive coronary angiography or CTCA within last 2 years and the previous investigation revealed obstructive coronary artery disease, or patient had either investigation within the last 5 years and the result was normal.
4. Previous recruitment to the trial;
5. Known pregnancy or currently breast feeding;
6. Inability to consent;
7. Further investigation for ACS would not in the patient's interest, due to limited life expectancy, quality of life or functional status;
8. Prisoners

4.4 CO-ENROLMENT

Co-enrolment will be permitted with non-interventional studies that involve data collection only. Co-enrolment with another interventional trial may be allowed provided this is not expected to place an undue burden upon participants and their families and will not compromise the primary end-point of either trial. Consideration will also be given to the total exposure to ionising radiation should additional studies require further exposure. Co-enrolment will only be permitted with agreement of the Chief Investigators of both studies.

5 PARTICIPANT SELECTION AND ENROLMENT

5.1 IDENTIFYING PARTICIPANTS

The research nurses, where it is locally agreed that they are part of the clinical care team, will identify patients using triage information and clinical or electronic records in the Emergency Department, Cardiology Department or the Medical Assessment Unit. In this case, it is anticipated they would identify patients and make the first approach. Any member of the clinical team who has received general and trial specific training and is on the delegation log may also identify patients in this way.

If research nurses are not considered to be part of the direct care team locally, activities carried out prior to consent (including identification) will be carried out by a member of the direct care team.

Where research nurses are not considered to be part of the care team, the research nurse should ask a member of the direct care team to identify suitable patients and ask permission from the patient to be approached by the research nurse to discuss participation.

There will be no additional trial specific screening tests performed. The patient will receive routine acute clinical assessment including, as a minimum, a 12-lead ECG, vital signs measurement (pulse rate, non-invasive blood pressure, respiratory rate, conscious level, oxygen saturations and skin prick blood sugar) and admission routine blood tests including troponin and renal function. The results of these will inform trial eligibility and the patient may be approached as soon as these are available (normally in the first 2 hours after presentation). Patients may be approached up to 24 hours after presentation. This time period has been chosen as it allows the longest period for recruitment where the patient could be deemed to be receiving acute assessment i.e. up to the point where a 12-hour troponin result is being used by routine clinicians for acute decision making. Patient and clinician will be unaware of treatment allocation until after screening, consent and randomisation.

5.2 CONSENTING PARTICIPANTS

Potentially eligible participants who are willing to take part in the study will be asked to provide written informed consent. Consent will be obtained by trained members of the clinical team or members of the research team who have been delegated this responsibility. The Investigator is responsible for the delivery of processes to ensure informed consent is obtained before any protocol specific procedures are carried out. The decision of a patient to participate in clinical research is voluntary and should be based on a clear understanding of what is involved.

The patient (and if present and appropriate their accompanying relative) will be given a Patient Information Sheet, which will explain the aims of the trial and the potential risks and benefits of the study treatments. If necessary, a summary sheet will be provided first to provide a brief outline of the study and allow potential participants to decide whether or not they wish to proceed and before the full Patient Information Sheet is provided.

The patient (and if appropriate the accompanying relative) will be given enough time to consider the trial and ask questions regarding their participation in the trial. At most this could be an hour but may be only 10-15 minutes. Potential participants must receive adequate oral and written information. The oral explanation to the patient will be performed by the clinical research nurse or a trained and delegated member of the clinical team and must cover all the elements specified in the Participant Information Sheet and Consent Form. The patient must be given every opportunity to clarify any points they do not understand and, if necessary, ask for more information. The patient must be given sufficient time to consider all the information provided. It should be emphasised that the patient may withdraw their consent to participate at any time without loss of benefits to which they otherwise would be entitled. The participant will be informed and agree to their medical records being inspected by representatives of the sponsor(s).

The Investigator or delegated member of the trial team and the participant will sign and date the Informed Consent Form(s) to confirm that consent has been obtained. The original consent form will be filed in the Investigator Site File (ISF), the participant will receive a copy of this document and a copy filed in the participant's medical notes.

Capacity will be assessed by the Principal Investigator (PI) or a clinician responsible for the treatment of the participant. This assessment of capacity will be documented in the participant's medical records. The trial excludes patients who have "life threatening features" and therefore this will effectively exclude patients who lack temporary capacity due to their current illness. Patients with permanent incapacity will not be recruited.

5.3 SCREENING FOR ELIGIBILITY

All patients aged ≥ 18 years of age with suspected or confirmed ACS will be screened for eligibility. Ineligible and non-recruited patients will receive standard medical care.

Female patients of childbearing potential i.e. women who have experienced menarche, are pre-menopausal, have not been sterilised should be asked if they are pregnant prior to entry into the trial. If the patient is unsure, they should be given an hCG pregnancy test to confirm before randomisation.

An anonymised log will be kept for patients who were screened for the study and those who were subsequently found to be ineligible or who were not recruited. This data should be entered onto the e-CRF for central monitoring purposes. Further guidance about screening can be found in the RAPID-CTCA Screening guidelines.

5.4 RANDOMISATION

5.4.1. Randomisation Procedures

After assessment for eligibility and consent, the clinical research nurse or a delegated member of the clinical team will collect the baseline data necessary to complete the pre-randomisation information on RAPID-CTCA Admission CRF. Randomisation will be carried out using a web-based randomisation service (managed by the Edinburgh Clinical Trials Unit) that ensures allocation concealment. Randomisation will be carried out within 24 hours of arrival at the hospital. Once a patient is randomised, s/he will remain in the study and have all outcomes recorded regardless of compliance with randomised pathway allocation, unless s/he specifically withdraws consent to have data stored. Consented patients will be randomised on a 1:1 basis to CTCA in addition to standard care or standard care alone and will be stratified by study site.

5.4.2. Intervention Allocation

CTCA results will be available to the clinical team to support acute clinical decision making. It is anticipated that the provision of immediate CTCA with early reporting is likely to be variable across the centres. The intervention will be delivered by routine clinical staff. It is anticipated that 60-70% of patients will be recruited between 8.00 am and 6.00 pm and would be eligible for immediate CTCA [Goodacre S et al, 2011]. Patients recruited to the study and randomised to CTCA should receive a CTCA as soon as feasible, and normally on the day of, or day following randomisation providing this does not significantly delay routine processes of care including discharge. Where a clinical decision is made to discharge the participant before the scan takes place, they should be asked to return for ambulatory CTCA within 72 hours. The patient should receive clinical review in the ED, MAU or cardiology after the CTCA, and the CTCA result should be available to support this clinical decision making. Discharged patients will receive an appointment card detailing study contact details, the date, time, and location of their CTCA.

The results of the CTCA are likely to direct subsequent management. A guideline has been developed which will be available to clinicians to guide subsequent management dependent on the CTCA result. [Appendix 1]. A template GP letter is available to clinicians if they wish to use this to inform the GP about non-obstructive disease identified by the CTCA which may require secondary prevention being implemented by the GP.

Other interventions

All other management and admission or discharge decisions will be at the discretion of the treating clinicians. Sites will be requested not to use CTCA as part of the routine investigation of ACS and this will be closely monitored.

Blinding

This is an open trial. The patient, recruiting and treating clinicians and radiologist will not be blinded to the intervention including results. Outcome assessors, however, will be blinded to the intervention.

Follow up

Patients will be followed up using routine clinical notes and research contact with the patient by phone, email or post. A 3% loss to follow up (patient withdrawal and inability to retrieve data for the primary outcome from routine NHS records) is built into the sample size calculation for the primary outcome; all patients will be analysed for the primary outcome on an intention-to-treat basis. At Trusts where it is not possible to routinely get this data from the NHS records, the research team at site will attempt to contact the participant and/or their GP by telephone to gather the 12-month follow up data. All patients will be followed for 1 year.

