Measurement of costs/outcomes: Primary end-point will be one-year all-cause death or subsequent type 1 or type 4b MI at one year, measured as time to first such event. Secondary endpoints: Key Secondary Endpoints : 1. Coronary Heart Disease (CHD) death or subsequent non-fatal MI; 2. Cardiovascular Disease (CVD) death or subsequent non-fatal MI; 3. Subsequent non-fatal MI; 4. Coronary Heart Disease death; 5. Cardiovascular death; 6. All-cause death. Other Endpoints; Coronary Heart Disease (CHD) death or subsequent non-fatal MI (type 1 or 4b); Subsequent Non-fatal MI (type 1 or 4b); Non-cardiovascular death; Invasive coronary angiography; Coronary revascularisation; Percutaneous coronary intervention; Coronary artery bypass graft; Proportion of patients prescribed ACS therapies during index hospitalisation; Proportion of patients discharged on preventative treatment or have alteration in dosage of preventative treatment during index hospitalisation; Length of stay for index hospitalisation; Representation or rehospitalisation with suspected ACS/recurrent chest pain within 12 months after index hospitalisation; Chest pain symptoms up to 12 months; Patient satisfaction at 1 month; Clinician certainty of presenting diagnosis after CTCA; Quality of Life (measured by EQ-5D-5L up to 12 months). Adverse Events and Serious Adverse Events; Proportion of patients with alternative cardiovascular diagnoses identified on CTCA; Proportion of patients with non-cardiovascular diagnosis identified on CTCA; Radiation exposure from CTCA as trial intervention. Cost effectiveness: Estimated in terms of the lifetime incremental cost per quality-adjusted life year (QALY) gained.

Sample size: one-year all-cause death or subsequent MI for this patient group is $\sim 20\%$ (Mills et al, 2011). The original aim was to recruit 2424 evaluable patients (1212 per arm) to have 90% power to detect a 20% vs. 15% difference in one-year death or subsequent type 1 MI or type 4b MI rate, 2-sided $P < 0.05$. With a $\sim 3\%$ drop out rate, the sample size will be 2,500 patients. The revised aim is to recruit at least 1720 patients (not allowing for missing data), at least 1735 with expected loss to follow up rates,

which would provide the trial the opportunity to detect a 3.4% ARR at the current primary event rate of 6.8% with 80% power, 2-sided $P<0.05$.

Lay Summary

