5.4.3. Compliance and withdrawal of Study Participants

Study participants are free to withdraw from the trial at any time. Reasons, if given, will be recorded and data collected up to that time point may be used in the final analyses, unless the patient specifically requests that their data are not used. If the patient withdraws consent to have their data stored, then this will be documented on the trial CONSORT flow diagram as 'withdrawn' and their data will not be used in the final analyses. Patients may withdraw from participation in active follow up but data will continue to be collected unless the patient requests otherwise. The patient may be willing to give a reason for withdrawal, but this is not obligatory.

Crossover

Any patient in the control group that has a CTCA as part of routine care within 30 days of randomisation will be defined as a crossover and does not need to be recorded as a deviation.

Non-adherence

This will be defined as to have occurred in any participant not receiving a reported CTCA if randomised to it within 72 hours of the randomisation and this would be recorded as a deviation. This allows ambulatory CTCA to be delivered when appropriate.

Individual site retention, crossover and non-adherence will be monitored and reviewed at the Project Management Group and Trial Steering Committees meetings.

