8. STATISTICS AND DATA ANALYSIS

Statistical Analysis

The trial will be reported on an intention-to-treat basis. The primary outcome is defined as first event of all cause death or subsequent non-fatal MI type 1 or 4b. Time to primary outcome is defined as time from randomisation to primary outcome. Patients discontinuing the study (for any reason) prior to reaching primary outcome will have their time to primary outcome censored at the last contact date. The relationship between intervention and the primary outcome will be analysed using Cox proportional hazard regression adjusted for study site (used to stratify the randomisation), baseline GRACE score, and previous CAD. The results will be expressed as a hazard ratio with the corresponding 95% confidence intervals and p-value. The individual elements of the composite primary outcome will be reported separately. Subgroup analysis on the primary outcome is planned for age, sex, baseline GRACE score, previous CAD, baseline ECG result, baseline troponin concentration, and presentation to a study site with or without on-site invasive coronary angiography facilities. These will be assessed by examining the effect of entering the treatment by subgroup interaction into the Cox regression model. Secondary outcomes will be analysed using appropriate methods: logistic regression for binary outcomes and linear regression for normally distributed continuous outcomes, adjusted as described above. Continuous outcomes that are not normally distributed will be analysed using appropriate nonparametric techniques. Every effort will be made to minimise missing data, and our primary analysis will be a complete case analysis. If there is a sufficient level of missing data for it to affect our conclusions, a multiple imputation analysis will be undertaken, using clinically appropriate variables, as a sensitivity analysis. Significance testing will use a hierarchical approach – for the primary outcome and the key secondary outcomes, statistical significance will be declared if the outcome in question, and all prior outcomes listed, have $p < 0.05$. P-values will be reported for all other outcomes but will not be declared to be significant.

A full statistical analysis plan will be written during the trial and finalised prior to database lock.

Economic analysis

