SCOT-HEART	Trial acronym for 'Scottish Computed Tomography of the Heart' trial
SD	Standard Deviation
SOP	Standard operating procedure
SPO2	Peripheral capillary oxygen saturation
TNK/TPA	Tenecteplase/Tissue plasminogen activator
TSC	Trial Steering Committee
U	Units
Y/N	Yes/No

1. Introduction

This document details the criteria to be used for the definition of the analysis populations and the statistical methodology for analysis for the RAPID-CTCA trial, a randomised controlled trial of early computed tomography coronary angiography (CTCA) in patients presenting with suspected/confirmed acute coronary syndrome (ACS) to Emergency Departments (ED) and Medical Assessment Units.

This document has been compiled according to the Edinburgh Clinical Trials Unit (ECTU) standard operating procedure (SOP) "Statistical Analysis Plans" ECTU_ST_04 and has been written based on information contained in the study protocol version 7.0, dated 24 February 2020.

RAPID-CTCA is a multicentre, randomised, parallel-group open trial. Randomisation is at the individual level with a 1:1 allocation ratio, and is stratified by study site. Patients are randomised to either CTCA in addition to standard care or standard care alone. The aim was originally to recruit 2,500 patients in about 30 NHS tertiary and district hospitals (with or without on-site coronary angiography facilities) with emergency departments, acute medical, radiology, and cardiology services. This was updated to a size of at least 1735 in protocol version 7.

2. Statistical Methods section from the protocol

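### Protocol 5.4.2 says a 3% loss to follow-up is built into the sample size, but the current step from 1720 to 1735 allows only about 0.9%

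*Protocol*

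**What the plan says.** Three parts of the protocol bear on the loss allowance.

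- **Section 5.4.2, follow-up paragraph.** In the present tense, and without reference to any particular version of the design, it says: "A 3% loss to follow up (patient withdrawal and inability to retrieve data for the primary outcome from routine NHS records) is built into" the primary-outcome sample size.
- **Section 4.1.** For the original design: "With a 3% drop out rate, the sample size would have been 2,500 patients". For the current design: "at least 1720 patients (not allowing for missing data), at least 1735 with expected loss to follow up rates". No percentage accompanies the current totals.
- **Summary, sample size.** It mentions the roughly 3% drop-out with the original aim, then continues: "The revised aim is to recruit at least 1720 patients (not allowing for missing data), at least 1735".

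The SAP introduction confirms which target is in force: "This was updated to a size of at least 1735 in protocol version 7".

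**The concern.** Section 5.4.2 is body text of the current protocol, not an amendment log, so a reader takes 3% as the allowance inside the current target. Section 4.1 attaches 3% only to the design that was replaced. The likeliest explanation is a sentence left unchanged when the target was cut from 2,500 to 1735.

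The expected loss rate is a basic sample-size assumption. Here the only rate stated without being tied to the old design does not fit the current totals, and the rate that was used is not given. Anyone who tries to rebuild 1735 from 1720 and 3% will fail. Section 5.4.3 has site retention reviewed by the Project Management Group and the Trial Steering Committee. If they took their benchmark from 5.4.2, they would believe that a 3% loss is already covered.

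**Working it through.** **Inputs (Protocol 4.1 unless noted).** Original design: 20% vs 15%, 90% power, 2424 evaluable, 2,500 with 3% drop-out. Current design: overall event rate 6.8%, absolute reduction 3.4%, 80% power, 1720 before loss and 1735 after. Both use two-sided 5%. Allocation is 1:1 (5.4.1).

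**Formula.** Two proportions, pooled variance under the null, no continuity correction, per arm:

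n = [1.960 × √(2p̄(1−p̄)) + z_power × √(p1(1−p1) + p2(1−p2))]² / (p1−p2)²

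Inflation for loss d: N/(1−d).

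**Step 1: reproduce the original design.** With 20% vs 15% and z_power = 1.282, n = 1211.5, so 1212 per arm and 2424 in total. Then 2424/0.97 = 2499, stated as 2,500. The 3% fits.

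**Step 2: reproduce the current design before loss.** Section 4.1 describes 6.8% as the overall rate in the first 716 participants. With a 3.4-point difference centred on 6.8%, the arms are 8.5% and 5.1%, a relative risk of 0.6, which is one of the values listed in 4.1. With z_power = 0.842, n = 859.4, so 860 per arm and 1720 in total, an exact match. Reading 6.8% as the control rate (6.8% vs 3.4%) gives 1314, which does not match.

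**Step 3: the allowance in the current target.**

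- Implied loss: 1 − 1720/1735 = 15/1735 = 0.86%.
- Target needed for 3%: 1720/0.97 = 1773.2, so 1774.
- Gap: 1774 − 1735 = 39 patients.

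**Step 4: could rounding explain it?** Assume 1720 is exact and 1735 was rounded to the nearest 5, so that the true figure lies between 1732.5 and 1737.5. The implied loss is then between 1 − 1720/1732.5 = 0.72% and 1 − 1720/1737.5 = 1.01%.

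**Step 5: could 3% have been applied only to participants beyond the 716 already followed?** 716 + (1720 − 716)/0.97 = 716 + 1035.1 = 1751, which is still not 1735.

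**Step 6: power if 3% of 1735 were lost.** 3% of 1735 is 52 patients, leaving 1683.

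*Two-proportion power, 8.5% vs 5.1%:*

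| Patients analysed | Power |
|---|---|
| 1720 | 80.0% |
| 1735 | 80.4% |
| 1683 | 79.2% |

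*Schoenfeld, closer to the planned Cox analysis:* HR = ln(1−0.051)/ln(1−0.085) = 0.589. Events for 80% power = 4 × (1.960 + 0.842)²/(ln 0.589)² = 112.3, so 113.

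| Scenario | Expected events | Power |
|---|---|---|
| No loss | 1735 × 0.068 = 118.0 | 81.9% |
| 3% lost, contributing half a year each (assumption) | 1735 × 0.985 × 0.068 = 116.2 | 81.3% |
| 3% lost, contributing nothing | 1683 × 0.068 = 114.4 | 80.8% |

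**The case against.** The best case against raising this is that nothing follows from it. Sections 4.1 and the Summary, which set the sample size, already separate the two designs, and the SAP confirms 1735. No document sizes the trial from the remark in 5.4.2. Participants who leave early still count up to that point: "data collected up to that time point may be used in the final analyses", and those who discontinue "prior to reaching primary outcome will have their time to primary outcome censored at the last contact date". SAP 4.4 records that missing data are low. On the events-based calculation even a full 3% loss leaves power above 80%. On this view the sentence is a leftover and the point is editorial.

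Most of that stands, and it is why the point is rated as minor. It does not make the sentence true: 5.4.2 gives the current target a property it does not have, in text that nothing marks as historical.

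A second objection is that both totals are floors and the revised rate is not stated, so 0.86% should not be treated as the sponsor's figure. That is fair. The secure statement is that the allowance is not 3%; 0.86% is what the two totals imply. Since the protocol itself presents the difference between the totals as the allowance for loss, the fact that they are minima does not rescue 3%.

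A third objection is that this is a mismatch of text, not a miscalculation. That is also fair: 2424, about 2,500 and 1720 all reproduce. The fault is that 3% in one section cannot be reconciled with the totals in another.

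**Conclusion.** The concern holds. The 3% in Protocol 5.4.2 belongs to the replaced 2,500-patient design. The current totals contain an allowance of about 0.86% (0.7% to 1.0% if 1735 was rounded to the nearest 5), and a 3% allowance would have required 39 more patients.

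The contradiction needs no modelling assumption: it is the ratio of two figures in section 4.1 set against a percentage in 5.4.2. The inferred rate rests on taking the step from 1720 to 1735 as the whole allowance. The power figures rest on 8.5% vs 5.1%, which is supported by its exact reproduction of 1720.

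The practical effect is small: at most 0.8 points of power below the 80% target on the two-proportion formula, none below it on the events-based formula, and no change to the analysis. It is a misstated design assumption that should be corrected, not a threat to the trial's conclusions.

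**What to change.** - **Section 5.4.2:** replace 3% with the loss rate actually used to set 1735. The protocol's own totals imply about 0.9%; the sponsor should confirm the figure.
- **Section 4.1 and the Summary:** state that rate next to 1735, in place of the unspecified reference to expected loss rates.
- **If the sponsor still expects 3%:** 5.4.2 should say plainly that 1735 does not include that allowance.

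The cost is a few words in three places. The first edit alone removes the contradiction; the other two let a reader reproduce 1735. Under section 12.1 a protocol change goes to the ethics committee and local R&D, so the correction is best carried with another amendment. It needs no extra patients and no change to the SAP or the analysis.
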